### 14.1 Study Design/Endpoints

This is a Phase I/II study of Irinotecan and SGI-110 in patients with locally advanced or metastatic colorectal cancer. The dose escalation portion of the study will be used to determine the preferred dose of SGI-110, 30mg/m^2, 45 mg/m^2 or 60 mg/m^2, in combination with Irinotecan. The second portion of this study will be an open-label randomized phase II study with one arm receiving combination SGI-110 plus Irinotecan at the recommended dose from phase 1 (determined to be SGI-110 45mg/m^2, Irinotecan 125mg/m^2, with mandatory growth factor support) and the other arm receiving Regorafenib or TAS-102 at the standard commercial dose. The primary objective of the study is based on a comparison of PFS in the SGI-110 arm to that in the Regorafenib or TAS-102 arm, the two approved standard of care drugs in this setting. The primary endpoint for the Phase II study will be progression free survival (PFS). The study will randomize patients to the SGI-110 versus Regorafenib or TAS-102 at a ratio of 2:1. The randomized Regorafenib or TAS-102 group will provide information about PFS with the standard of care drugs to verify assumptions made in the design of the study.

**Phase I primary objective:** To assess safety and tolerability of Irinotecan in combination with SGI-110 in patients with advanced colon cancer. Determine the maximum tolerated dose (MTD) of Irinotecan in combination with SGI-110 and recommend a dose for phase II study.

**Phase I secondary objectives:**

1. To assess changes in global methylation and expression at the tumor level with SGI-110 and Irinotecan treatment.
2. To assess the pharmacokinetics of SGI-110 in metastatic colon cancer patients and correlate with changes in global methylation.

**Dose Escalation:** Three dose levels of SGI-110, 30mg/m^2, 45 mg/m^2 and 60 mg/m^2, will be tested in combination with Irinotecan in this portion of the study. Dose level 1 will be IRI 125 mg/m^2

[figure not shown]
CONFIDENTIAL

This document is confidential. Do not disclose or use except as authorized.

days 8 and 15 and SGI-110 45 mg/m^2 days 1-5 and dose level 2 will be IRI 125 mg/m^2 days 8 and 15 and SGI-110 60 mg/m^2 days 1-5; dose level 3 would be SGI-110 at 60 mg/m^2 days 1-5 with IRI at 125 mg/m^2 days 1, 8, and 15. Starting with dose level 1, three patients will be treated in a standard 3+3 dose escalation design. If none of the first three patients experiences a DLT then the next three will be treated using the next higher dose. If one of the first three has a DLT, an additional three patients will be enrolled at that level. If only one of six develops a DLT, then the dose will be escalated for the next three patients. If two or more of the six have a DLT, then the dose will be de-escalated to the previous dose where an additional three patients will be treated. The MTD is defined as the highest dose at which 0 or 1 dose-limiting toxicities are observed in six patients. A total of 6 patients will be treated at the MTD. The target toxicity with this type of design is less than 30%.

If there are two DLTs at the first dose level, a decreased dose schedule of SGI-110, which is less myelosuppressive, will be considered with a similar 3+3 escalation of SGI-110. The next dose level below dose level 1 (dose level -1) would consist of IRI 125 mg m^2 days 8 and 15 and SGI-110 30 mg/m^2 days 1-5. If no DLTs are encountered with dose level -1, the next three patients will be entered at dose level 1G, or IRI 125mg/m^2 days 8, and 15 and SGI-110 45mg/m^2 days 1-5. If one of the three patients has a DLT at dose level -1, an additional three patients will be enrolled at that level. If only one of six develops a DLT, then the dose will be escalated for the next three patients to dose level 1G. If two or more DLTs out of 6 are encountered at Dose level -1, at least an additional 3 patients will be enrolled at the lower dose level, Dose level -1G. If 0/3 or 1/6 DLTs occur on Dose level -1G, the next 3 patients will be dose escalated to Dose level 1G. If 2 or more DLTs out of 6 are experienced at Dose level -1G, the MTD will have been exceeded.

Figure 14.1.1. De-escalation Schema.

CONFIDENTIAL

This document is confidential. Do not disclose or use except as authorized.

**Sample size/accrual rate for dose escalation:** The accrual rate for the dose escalation portion of this study is expected to be 3 patients per month. The maximum sample size in the dose escalation portion of the study could be 12 patients. If no patients experience a DLT, 9 patients will be enrolled.

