## **5 TREATMENT PLAN**

### **5.1 Overall Study Design**

CONFIDENTIAL

This document is confidential. Do not disclose or use except as authorized.

There will be two stages in this study: A phase I lead-in (Stage 1) followed by a randomized, controlled, open-label stage (Stage 2). Treatment will be administered on an outpatient basis

### 5.1.2 Stage 1

Stage 1 will be a traditional phase I study with a standard 3+3 design. A maximum of twenty-one eligible subjects will be enrolled to the phase I study. Study drugs will be escalated per the schema to maximize the dose of drugs when given concurrently. Patients will be treated with combined therapy immediately. Each cycle will last 28 days. All patients enrolled at each dose level will be evaluated for DLT for the purpose of determining the MTD. The dose escalation scheme is shown below.

Table 2: Dose escalation schedule

Dose Level	SGI-110 (SC)	Irinotecan (IV)	Growth Factor Support with Filgrastim (or institutional equivalent) and/or Pegfilgrastim (SC)
-1G	30 mg/m  days 1-5	125 mg/m  days 8 and 15 each cycle	Filgrastim 5mcg/kg/day Cycle 1 Days 9-14 and peg-filgrastim 6mg D16, additional growth factor support during Cycle 1 and subsequent cycles per clinician judgment
-1	30 mg/m  days 1-5	125 mg/m  days 8 and 15 each cycle	Per clinician judgment
1 (starting dose level)	45 mg/m  days 1-5	125 mg/m  days 8 and 15 each cycle	Per clinician judgment
1G	45 mg/m  days 1-5	125 mg/m  days 8 and 15 each cycle	Filgrastim 5mcg/kg/day Cycle 1 Days 9-14 and peg-filgrastim 6mg D16, additional growth factor support during Cycle 1 and subsequent cycles per clinician judgment
2	60 mg/m  days 1-5	125 mg/m  days 8 and 15 each cycle	Per clinician judgment
3	60 mg/m  days 1-5	125 mg/m  days 1, 8 and 15 each cycle	Per clinician judgment

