At least three patients will be treated at each dose level. If 0/3 patients exhibits a dose-limiting toxicity (DLT) after 4 weeks, the next patient will be treated at the next dose level. If one patient exhibits a DLT related to the study agent(s), the cohort will be expanded to up to 6 patients. If 1 of 6 patients exhibits a DLT related to the study agent(s), then the next patient will enroll at the next dose level. If 2 of 3-6 patients exhibit a DLT related to the study agent(s), the MTD is considered to have been exceeded and at least 6 patients will be entered at the dose level below the one at which DLT is defined. If this occurs on first dose level, the dose of SGI-110 will be reduced to 30 mg/m^2 days 1-5 (Dose level -1). If no DLTs are encountered at Dose level -1, the next 3 patients will be entered at the next dose level, Dose level 1G. If one DLT is encountered at Dose level -1, this dose level will be expanded to 6 total patients at Dose level -1. And if two or more DLTs are encountered at Dose level

CONFIDENTIAL

This document is confidential. Do not disclose or use except as authorized.

-1, at least an additional 3 patients will be enrolled at the lower dose level, Dose level -1G. If 0/3 or 1/6 DLTs occur on Dose level -1G, the next 3 patients will be dose escalated to Dose level 1G. If 2 or more DLTs out of 6 are experienced at Dose level -1G, the MTD will have been exceeded. Dose escalations will occur no sooner than 4 weeks after the last patient on the dose level has begun therapy to allow for full assessment of DLT.

Table 3: Dose escalations schema

Number of Patients with DLT at a Given Dose Level	Escalation Decision Rule
0 out of 3	Enter 3 patients at the next dose level.
$\geq 2$	Dose escalation will be stopped. This dose level will be declared the maximally administered dose (highest dose administered). Three (3) additional patients will be entered at the next lower dose level if only 3 patients were treated previously at that dose.
1 out of 3	Enter at least 3 more patients at this dose level. 
 
• If 0 of these 3 patients experience DLT, proceed to the next dose level.
 
• If 1 or more of this group suffer DLT, then dose escalation is stopped, and this dose is declared the maximally administered dose. Three (3) additional patients will be entered at the next lower dose level if only 3 patients were treated previously at that dose.
 

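### The phase I maximum is 21 in section 5.1.2 and 12 in section 14.1; 12 is below what the escalation rules allow, and the no-DLT figure of 9 omits the six-at-MTD rule

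*Combined protocol and SAP*

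**What the plan says.** Section 5.1.2 (Stage 1) gives one ceiling: "A maximum of twenty-one eligible subjects will be enrolled to the phase I study". Section 14.1, in the paragraph on sample size and accrual for dose escalation, gives another: "The maximum sample size in the dose escalation portion of the study could be 12 patients". It continues: "If no patients experience a DLT, 9 patients will be enrolled".

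The rules that determine these counts stand in the same two sections. Section 14.1 says "Starting with dose level 1, three patients will be treated in a standard 3+3 dose escalation design", and names levels 1, 2 and 3 as the upward ladder. One DLT among three patients brings three more at that level. Two or more DLTs send the trial down a level. If level 1 is exceeded, the next level is -1; if -1 is exceeded, -1G; a cleared -1 or -1G leads to 1G. Section 14.1 also requires: "A total of 6 patients will be treated at the MTD". The last row of Table 3 in section 5.1.2 likewise asks for at least six at the recommended phase 2 dose. Table 2 lists six levels in all: -1G, -1, 1, 1G, 2 and 3.

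**The concern.** A 3+3 design has no power calculation, so its sample size is simply a count that follows from the escalation rules. Here two sections give different maxima for the same phase. The smaller one looks too small for a ladder of three upward levels with a further branch below level 1. The no-DLT figure looks like three cohorts of three, without the patients needed to bring the MTD up to six.

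These figures are the enrolment limits against which phase I conduct is reported. Any phase I enrolment of 13 to 21 would respect section 5.1.2 and exceed section 14.1.

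**Working it through.** **Inputs**

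- Start at level 1 in cohorts of three; upward levels 1, 2 and 3 (section 14.1, Dose Escalation).
- One DLT in three: three more, so six at that level (section 14.1; Table 3).
- Two or more DLTs: three more at the level below if only three were treated there before (Table 3; section 14.1 is similar).
- Level 1 exceeded leads to -1; -1 exceeded leads to -1G; -1 or -1G cleared leads to 1G (sections 5.1.2 and 14.1).
- Six patients at the MTD (section 14.1).
- Assumption: no level takes more than six. Some rules say *at least*, so the text itself sets no strict upper bound.

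**Formula.** N = sum of the patients at each level opened, each level holding 3 or 6.

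**1. Reproducing the section 14.1 figures.** A ladder of only two levels gives a maximum of 6 + 6 = 12 and a no-DLT count of 3 + 6 = 9. Both match. On the present three upward levels, 9 appears only if the six-at-MTD rule is left out (3 + 3 + 3 = 9), and 12 does not appear as a maximum.

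**2. No DLT, current rules.** Three at level 1, three at level 2, and three plus three at level 3: 3 + 3 + 6 = 12.

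**3. Maximum, current rules.**

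| Route | Sum | N |
|---|---|---|
| Levels 1, 2, 3 only | 3 × 6 | 18 |
| Level 1 fails before level 2 opens: 1, -1, -1G, 1G | 4 × 6 | 24 |
| All six levels filled | 6 × 6 | 36 |

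A route to 36 runs as follows:

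- Level 1 has 0/3 and level 2 has 0/3.
- Level 3 has 2/6.
- Level 2 is brought up to six and shows 2/6.
- Level 1 is brought up to six and shows 2/6.
- Level -1 has 2/6 and level -1G has 1/6.
- Six patients are then treated at 1G.

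Listing every cohort outcome under these rules gives the same no-DLT count and the same three maxima.

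**4. The figure of 21.** It can arise, for example as 6 (level 1) + 6 (level -1) + 3 (level -1G, 0/3) + 6 (level 1G) = 21. It is not the maximum on any of the three bases in the table.

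**5. Differences.** The stated 12 falls short by 18 − 12 = 6, 24 − 12 = 12, or 36 − 12 = 24, depending on the basis. The stated 21 is above 18, but short of 24 by 3 and of 36 by 15. The stated 9 is short of 12 by 3.

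**The case against.** The best defence is that nothing now turns on these numbers. Section 5.1.3 records that the MTD was determined at level 1G as of December 2015, and no phase II sample size, power or decision rule uses the phase I count. That stands, and it limits the importance of the point. It does not make two contradictory maxima consistent.

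A second defence is that 21 is an accrual ceiling set below the theoretical worst case. That is possible, since 21 occurs on a permitted route. A reader might infer that 21 is an arithmetic error; the documents do not show that. They also do not call it a cap, do not carry it into section 14.1, and do not say what happens if the rules call for more.

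Third, 9 may count only the escalation cohorts. That is a likely origin, but the sentence gives the number enrolled, and the same section requires six at the MTD.

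Two stronger readings should be set aside:

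- A reader might infer that section 5.1.2 contradicts itself on how many patients enter the lower level. Its text says "at least 6 patients will be entered at the dose level below the one at which DLT is defined", while Table 3 says "Three (3) additional patients will be entered at the next lower dose level if only 3 patients were treated previously at that dose". If the six is a total, then 3 + 3 = 6 and the two agree. Table 3 uses the same verb for a total at the recommended phase 2 dose.
- A reader might infer that a limit of 12 rules out reaching 1G. It does not: three at level 1 with two DLTs, three at level -1 with none, and six at 1G make 12. That route simply leaves no room for any expansion on the way.

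**Conclusion.** The point holds as a minor consistency and reporting error. The two maxima conflict. Twelve cannot be the maximum, because the upward ladder alone allows 18. Nine with no DLT should be 12 under the plan's own six-at-MTD rule.

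A reader might infer that 24 is the single correct maximum. The rules do not give that: 24 applies only when level 1 fails before level 2 opens, and the full set of rules reaches 36. Both figures assume at most six patients per level.

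That 12 and 9 both fit a two-level ladder suggests text left unchanged when levels were added, but this is inference. Nor can it be concluded that phase I exceeded a limit, since the documents do not report how many patients were enrolled. Phase II power is unaffected.

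**What to change.** Replace the figures in sections 5.1.2 and 14.1 with one reconciled set:

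- 12 patients if there is no DLT.
- A maximum stated with its assumption: 18 on levels 1 to 3, 24 when level 1 fails before level 2 opens, or 36 if all six levels fill to six.
- If 21 is meant as an accrual cap, label it as a cap in both sections and state what happens if the rules call for more patients.

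Report the number actually enrolled in phase I, by dose level. The cost is a text correction; no escalation rule, analysis or phase II figure has to change.

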**Analysis of primary objective in dose escalation cohort:**

The number of dose-limiting toxicities at each dose level will be reported. Additional toxicity frequencies by type and grade will be summarized by dose level for all doses.

**Analysis of secondary objectives in dose escalation:**

- 1) The design of this study will allow assessment of global and candidate gene methylation differences at the tumor level. We hypothesize that Irinotecan resistance may be reversed with the use of the demethylating SGI-110 therapy. Changes in global methylation by LINE-1 will be assessed in post-treatment biopsy specimens in the dose escalation cohort for proof of the effect of SGI-110. Changes will be plotted by dose level and overall using boxplots of the log transformed raw data. A paired t-test, or the nonparametric Wilcoxon signed rank test, will be used to test if the changes are significantly different from zero. Similar analyses will be used to assess gene expression changes in WRN, DR1, TPAF2E, DEXI, BNIP3, and MED1.
- 2) Pharmacokinetic (PK) sampling studies are proposed for all participating patients who undergo pharmacodynamic endpoints. Single dose PK samples will be collected on Cycle 1, Day 1, at the following time points: pre-dose 0.25, 0.5, 1, 1.5, 2, 3, 4, 6, and 8 hr. The following PK parameters describing the concentration time profile of SGI-110 will be calculated: total exposure will be calculated as area under the plasma concentration-time curve (AUC) using the linear trapezoidal rule by using noncompartmental methods (Winonlin, version 5.3) and/or compartmental modeling (Adapt II, release 4.0). Other parameters such as maximum concentration ( $C_{max}$ ), time to maximal concentration ( $T_{max}$ ) and half-life ( $T_{1/2}$ ) will also be calculated.  $C_{max}$  and  $T_{max}$  will be obtained from the data, while the half-life will be calculated as  $0.693/k$ , where  $k$  is the slope of terminal elimination phase. Associations between SGI-110 exposure parameters ( $C_{max}$  and AUC) and pharmacodynamic endpoints (i.e., global methylation changes and toxicity) will be assessed using appropriate non-parametric statistical tests.

**Moving to Phase II Component:** Our hypothesis is that SGI-110 treatment will sensitize colon cancer patients to retreatment with irinotecan. Accordingly, it will be important to see that the dose of SGI-110 that is at the MTD does have pharmacodynamics effects at the tumor level. Patient tumor biopsies post-treatment will be analyzed by LINE assay for demethylation to assess for at least 10% demethylation from baseline in the tumor biopsies. We aim to see this level of demethylation in at least 60% of post-treatment biopsies as previously described in phase O studies.

**Phase II primary objective:** Evaluate the progression free survival (PFS) in patients receiving combination SGI-110 plus Irinotecan compared to standard of care treatment with regorafenib or TAS-102. Events are defined as disease progression or death from any cause. All patients treated

CONFIDENTIAL

This document is confidential. Do not disclose or use except as authorized.

on protocol will be included in the determination of PFS, regardless of treatment modification or discontinuation.

Epigenetic therapy may take several cycles to exert its maximal benefit, and preclinical data has demonstrated initial tumor growth is possible prior to tumor shrinkage. Patients on treatment with SGI-110 and IRI will be allowed to remain on study if their tumor progresses on RECIST 1.1 criteria if they are 1) clinically stable, 2) their provider feels it would be in their best interest, and 3) the patient is informed of scan results and consents to remain on treatment. In this circumstance, they will be reimaged on schedule after 2 further cycles. If this subsequent imaging confirms progressive disease, the date of the progression even will be dated to the first (initial) scan date that progression was first documented.

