### 1.3 Secondary Objectives

#### Phase I Component: Stage I

- To assess changes in global methylation and expression at the tumor level with SGI-110 and irinotecan treatment
- To assess for pharmacokinetic interactions of SGI-110 and irinotecan
- To assess for correlation between disease response and drug exposure

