### 2.1.5 Human pharmacokinetics

The PK of SGI-110 and decitabine are being evaluated in Study SGI-110-01. Decitabine forms from SGI-110 as it undergoes cleavage by phosphodiesterase (PDE) enzymes. SGI-110 after SC injection undergoes efficient conversion to decitabine and delivers decitabine exposures as measured by AUC that are equivalent or higher than those achieved by IV decitabine infusion at 20 mg/m^2, while maintaining significantly lower decitabine Cmax. It is hypothesized that lower Cmax may be associated with less toxicity.

Due to slower release of decitabine from SGI-110, the effective half-life of decitabine after SC SGI-110 is prolonged and the observed decitabine exposure window is longer (8+ hrs) compared to IV (3-4 hrs). At Cohort 6, doses of 90 mg/m^2 for the daily regimen and 125 mg/m^2 for weekly, the observed decitabine AUCs were approximately 1.41 and 1.77 fold higher than with IV decitabine at the approved dose of 20 mg/m^2 IV, whereas Cmax levels were only at 0.35 and 0.44-fold for the daily and weekly regimens, respectively. It is hypothesized that longer exposure to decitabine may allow more drug to be incorporated into the DNA thus resulting in better hypomethylation and better biological activity. Clinical drug-drug interaction studies have not been conducted with SGI-110. *In vitro*, SGI-110 does not inhibit the activity nor induce levels of major human CYP enzymes, hence, the likelihood of CYP-mediated drug-drug interactions with SGI-110 is remote.

[figure not shown]

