### 8.2 Pharmacokinetic Studies

Pharmacokinetic evaluation will be conducted during Phase 1 only, in all subjects in order to evaluate exposures of SGI-110 and decitabine in the disease population. SGI-110 does not inhibit nor induce CYP3A4, which is the major contributing enzyme to irinotecan metabolism. As such,

CONFIDENTIAL

This document is confidential. Do not disclose or use except as authorized.

irinotecan pharmacokinetics will not be evaluated in this study as its exposures are not expected to be affected by SGI-110.

Pharmacokinetics of SGI-110 and decitabine will be assessed from plasma concentrations.

Plasma samples will be prepared from blood drawn at the following time-points:

Cycle 1, Day 1: pre-dose, 15 min, 30 min, 60 min, 90 min, 2 hr, 4 hr, 6 hr and 8 hr post-dose.

Sampling windows are up to 10% of protocol specified time point but no more than 1 hour.

Details for procedure for PK sample collection are included below.

Plasma samples will be appropriately labeled and shipped for analysis to:

[name], Sample Coordinator

Frontage Laboratories, Inc.

[name]

[name]

P: [contact]

Email : <[contact]>

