5. Pharmacokinetic (PK) sampling studies are proposed for all participating patients who undergo pharmacodynamic endpoints. Single dose PK samples will be collected on Cycle1, Day 1, at the following time points: pre-dose 0.25, 0.5, 1, 1.5, 2, 3, 4, 6, and 8 hr. The following PK parameters describing the concentration time profile of SGI-110 and Irinotecan will be calculated: total exposure will be calculated as area under the plasma concentration-time curve (AUC) using the linear trapezoidal rule by using noncompartmental methods (Winonlin, version 5.3) and/or compartmental modeling (Adapt II, release 4.0). Other parameters such as maximum concentration ( $C_{max}$ ), time to maximal concentration ( $T_{max}$ ) and half-life ( $T_{1/2}$ ) will also be calculated.  $C_{max}$  and  $T_{max}$  will be obtained from the data, while the half-life will be calculated as  $0.693/k$ , where  $k$  is the slope of terminal elimination phase. Associations between SGI-110 exposure parameters

CONFIDENTIAL

This document is confidential. Do not disclose or use except as authorized.

(Cmax and AUC) and pharmacodynamic endpoints (i.e., global methylation changes toxicity and toxicity) will be assessed using appropriate non-parametric statistical tests.

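### Section 14.1 relates methylation change and toxicity to SGI-110 exposure only, leaving out decitabine, the active form, which is assayed in the same samples

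*Combined protocol and SAP*

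**What the plan says.** **Analysis section.** Section 14.1, Analysis of secondary objectives in dose escalation, item 2, states: "The following PK parameters describing the concentration time profile of SGI-110 will be calculated". The parameters are AUC, Cmax, Tmax and half-life. The test that follows is of "Associations between SGI-110 exposure parameters", namely Cmax and AUC, against global methylation change and toxicity by non-parametric methods. Decitabine is not named.

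The objective served, item 2 of the Phase I secondary objectives in 14.1, is also worded for SGI-110: "To assess the pharmacokinetics of SGI-110 in metastatic colon cancer patients and correlate with changes in global methylation". Item 4 of the Phase II secondary objectives repeats it. Item 5 of the Analysis of secondary objectives for phase II has the same structure but adds irinotecan, not decitabine: "The following PK parameters describing the concentration time profile of SGI-110 and Irinotecan will be calculated". Its association test is again for SGI-110 alone.

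**PK methods.** Section 8.2 says: "Pharmacokinetics of SGI-110 and decitabine will be assessed from plasma concentrations". It gives the exposure of both as the purpose of sampling, and its collection guide labels one tube per time point for both analytes. It limits PK to phase 1 and excludes irinotecan PK.

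**Pharmacology.** Sections 2.1.1 and 6.1.4 call decitabine the active metabolite or active form. Section 2.1.5 says: "SGI-110 after SC injection undergoes efficient conversion to decitabine". The same section hypothesises that longer decitabine exposure gives better hypomethylation and that a lower decitabine Cmax may mean less toxicity.

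**The concern.** The two effects tested in 14.1, methylation change and toxicity, are the two that section 2.1.5 links by hypothesis to decitabine exposure and decitabine Cmax. Section 14.1 tests them against the parent compound. The decitabine concentrations will exist, but the analysis plan does not use them.

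Parent exposure stands in for decitabine only as far as the two are correlated between patients, and the documents give reason not to assume that the correlation is close. Section 2.1.1 says that SGI-110 resists cytidine deaminase while decitabine is deactivated by it. Differences between patients in deamination would then alter decitabine exposure without necessarily showing in SGI-110 AUC.

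At stake is how far a phase I secondary result can be interpreted. A weak SGI-110 association would not separate no exposure-effect relation from a relation blurred by the surrogate. Leaving the analyte open also allows decitabine to be brought in after the parent result is known.

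**Working it through.** The plan states no power or sample size for this analysis, so there is no figure to reproduce. The check has three parts.

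**1. The two sections side by side**

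| Question | Section 8.2 | Section 14.1 |
|---|---|---|
| Analytes, phase I | SGI-110 and decitabine | SGI-110 |
| Analytes, phase II | none (PK in phase 1 only) | SGI-110 and irinotecan |
| Irinotecan PK | not evaluated | parameters calculated (phase II item 5) |
| Exposure variable in association tests | not addressed | SGI-110 Cmax and AUC |

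No section says that decitabine exposure enters the association tests.

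**2. Does decitabine exposure simply scale with SGI-110?**

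Inputs: molecular weights of 580 and 228 Da (section 2.1.1), and decitabine AUC at 1.41 and 1.77 times that of IV decitabine 20 mg/m² after SGI-110 90 mg/m² daily and 125 mg/m² weekly (section 2.1.5, figures read as ratios).

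- Molar ratio: 580/228 = 2.54, in line with the stated 2.5.
- 90/2.54 = 35.4 mg/m² decitabine-equivalent; 35.4/20 = 1.77. Observed AUC against molar dose: 1.41/1.77 = 0.80.
- 125/2.54 = 49.1 mg/m²; 49.1/20 = 2.46. Observed AUC against molar dose: 1.77/2.46 = 0.72.

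Decitabine AUC was thus not a fixed multiple of SGI-110 dose across these two regimens. This compares groups and doses. It does not give the within-study correlation of parent and decitabine AUC, which appears nowhere in the documents.

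**3. Illustration of the loss**

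Assumptions, none from the documents: the correlation of decitabine exposure with effect is 0.6; SGI-110 relates to the effect only through decitabine; the parent-decitabine correlation ρ is 0.5 to 0.8; the test is two-sided at 5%.

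Sample size: section 5.1.2 gives a maximum of 21, while section 14.1 gives a maximum of 12, or 9 with no DLT. Both maxima are shown.

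Parent-effect correlation: r = 0.6 × ρ.

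Power for a rank correlation: Φ(atanh(r) × √(n−3) / √1.06 − 1.96). Without √1.06 this is the ordinary Fisher z figure.

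Example, n = 12 and ρ = 0.8: r = 0.48; atanh(0.48) = 0.523; 0.523 × 3 / 1.030 = 1.524; 1.524 − 1.96 = −0.436; Φ = 0.33.

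| Exposure variable | r | n = 12, rank | n = 21, rank | n = 21, Fisher z |
|---|---|---|---|---|
| Decitabine | 0.60 | 52% | 82% | 84% |
| SGI-110, ρ = 0.8 | 0.48 | 33% | 58% | 60% |
| SGI-110, ρ = 0.5 | 0.30 | 15% | 25% | 26% |

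With 9 patients the rank figures are 38%, 24% and 11%.

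**The case against.** **Decitabine PK is already planned.** Section 8.2 commits to evaluating decitabine exposure, so a reader who inferred that it will go unexamined would be mistaken. The gap is confined to the parameter list and the association sentence in 14.1. Item 5 for phase II, with its irinotecan PK that 8.2 excludes, suggests loose drafting and not a deliberate choice of analyte. This stands, but 14.1 is the text the analyst will follow.

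**SGI-110 is not the wrong variable.** A reader might infer that the trial would correlate effects with an irrelevant moiety. The documents do not support that. SGI-110 is the precursor, conversion is described as efficient, and a dose range of 30 to 60 mg/m² would itself tend to induce some correlation between parent and decitabine. Imperfect surrogate is the accurate description.

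**Nothing is decided on it.** A reader might infer that this association supports the activity of the phase II dose. It does not carry that weight. Under Moving to Phase II Component, activity is assessed directly by LINE demethylation, aiming for at least 10% in at least 60% of post-treatment biopsies. Section 5.1.3 records the phase II dose as set from the phase I MTD as of December 2015. This objection stands in full.

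**The power figures rest on assumptions.** True. At 12 patients the decitabine analysis would itself have only about 52% power, so the change improves interpretability more than it secures detection. Failed biopsies, which section 8.3.1 allows for, would lower the numbers further.

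**Sampling to 8 hours.** Section 2.1.5 gives a decitabine exposure window of 8 hours or more, so a reader might infer serious truncation of AUC. For SGI-110, with animal half-lives of 0.4 to 1 h (section 2.1.2), 8 h is at least eight half-lives and the remainder is negligible. For decitabine, assumed half-lives of 1 to 3 h with first-order absorption (half-life 0.25 to 0.5 h) leave about 1% to 19% beyond 8 h. Section 14.1 also permits compartmental modelling and estimates a terminal slope. What remains is a labelling question.

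**Conclusion.** The point holds as a mismatch between sections 8.2 and 14.1 with an analytical consequence: followed literally, the phase I exposure-effect analysis omits the moiety that the protocol itself hypothesises to act. This rests on the text and needs no assumption.

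The size of the loss is not known. The fall in power from about 52% to 15-33% (n = 12), or from 82-84% to 25-60% (n = 21), shows only what an imperfect surrogate could cost under the assumed correlations. With ρ near 1 there would be almost no loss.

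The consequence is limited to the interpretation of one phase I secondary analysis. The phase II PFS comparison, the dose already set and the pharmacodynamic check for moving on are unaffected. The phase I objective in section 1.3, "To assess for correlation between disease response and drug exposure", names no moiety and has no analysis in 14.1. That is a separate gap.

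**What to change.** In section 14.1, Analysis of secondary objectives in dose escalation, item 2:

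- derive AUC, Cmax, Tmax and half-life for both SGI-110 and decitabine;
- pre-specify decitabine AUC and Cmax as the main exposure variables for the associations with methylation change and toxicity, with the SGI-110 associations as supportive;
- state whether AUC is AUC0-8 or extrapolated and, if extrapolated, report the extrapolated percentage.

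Reconcile the PK wording of the Phase I secondary objectives (item 2), the Phase II secondary objectives (item 4) and the Analysis of secondary objectives (item 5) with section 8.2, which limits PK to phase 1, covers SGI-110 and decitabine, and excludes irinotecan PK.

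The documents do not say whether the phase I association analysis has already been run. If it has, report the decitabine analysis as added afterwards.

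The cost is an amendment to wording and a few more parameters computed from concentrations that section 8.2 already plans to measure. No extra samples, visits or assays are needed.
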